The activation status of T-cell populations may provide another indicator of cellular immunity potentially involved in pregnancy loss. The IL-2 receptor has been reported to be absent on T-cells in normal first trimester decidual tissues using immunohistochemical techniques [16]; however, using flow cytometry, CD3⁺CD25⁺ activated T-cells have been identified in decidual tissue [17]. CD69 is another early activation marker expressed on the surface of T-cells [18]. A proportion of T-cells constitutively expresses this marker throughout the menstrual cycle and in normal early pregnancy.

Approximately 60% of spontaneous abortions are attributable to numerically abnormal chromosomes in the developing conceptus [19], yet limited data to date addressing immunological phenomena in the decidua of miscarried women has compared their data relative to well-defined chromosomal abnormalities belonging to conceptuses. This is important since the chromosome abnormality trisomy 16, which occurs in 26% of all spontaneous abortions, is incompatible with life [20] and would thus be an undisputed cause of spontaneous abortion. Therefore, the purpose of our study was to determine whether decidual leukocyte subpopulations and their associated activation markers were different between women having miscarriage of either a trisomy 16 conceptus (47XY+16 or 47XX+16) compared with a chromosomally normal male conceptus (46XY) and compared with gestationally age-matched decidual tissues. Samples from presumably normal female conceptuses (46XX) were not chosen for study because of the inability to accurately differentiate from possible maternal cell contamination.

For managing with miscarriage or termination of pregnancy (TOP) in first trimester loss, ultrasound-guided manual vacuum aspiration (USG-MVA) is one of the treatment options. USG-MVA for the treatment of early pregnancy loss has been used for many decades. It had been reported that USG-MVA is safer, more cost-effective, and is associated with shorter hospitalization time and cost than surgical evacuation under general anesthesia [21, 22]. USG-MVA is a surgical technique of suction curettage. It is performed by using a hand held vacuum source (a syringe with barrel and plunger) attached to a uterine cannula [23, 24] The USG-MVA device works by aspirating the uterine content via the cannula into the syringe. Furthermore, product of conception derived from USG-MVA can be sent for karyotyping analysis.

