B. Study objectives and hypotheses

I. Objective

- (1) To investigate the immune cells profile in decidua derived from early pregnancy loss and correlate the result to the embryo karyotyping.
- (2) To investigate the genetic abnormality spectrum of early pregnancy loss by comprehensive next-generation-sequencing based approaches.

II. Hypotheses

- (1) Decidua tissue is different between euploidy pregnancy and aneuploidy pregnancy.
- (2) Except for well-known genetic abnormalities, early pregnancy loss can be attributed to various genetic etiologies, including cryptic structural rearrangements, absence of heterozygosity (AOH), and single-nucleotide variant (SNV), which can be detected by sequencing approaches.

C. Subjects:

Women undergoing ultrasound-guided manual vacuum aspiration (USG-MVA) will be recruited at Obstetrics and Gynaecology in The Prince of Wales Hospital

I. Inclusion Criteria

- (1) Women 18 years old or above
- (2) Women with miscarriage or TOP who are suitable candidates for MVA
 - first trimester miscarriage or TOP
 - No fetal heart beat or TOP in those with CRL 25mm
 - incomplete miscarriage or TOP with POG <5cm
 - hemodynamically stable,
 - tolerates well with speculum examination

II. Exclusion Criteria

(1) Women who are not feasible for the MVA procedure

- cervical stenosis
- fibroid uterus >12 weeks in size
- known uterine malformation
- bleeding disorder
- clinically sepsis
- inability to tolerate pelvic examination

(2) History of psychological/ psychiatric problem

(3) Patient refusal

D. Sample Size

There are two groups in this study: (1) women who miscarry or TOP with chromosomally normal fetus; (2) women who miscarry or TOP with chromosomally abnormal fetus.

There is no literature data on the difference in leucocytes profile between groups. In calculating the sample size required, we are making an assumption that the degree to which other leucocytes are affected, is similar to that of CD45+ cell count.

According to our pilot result, the CD45+ cell count was 89.7 ± 18.3 in decidual samples from miscarried women with abnormal karyotyping and 102.3 ± 20.2 in miscarriage women with normal fetal karyotyping, respectively. The sample size required for an alpha value of 0.05 and 80% power would be 50 in each arm. Therefore, a total of 100 subjects will be recruited.

E. MVA procedure

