The Drop-seq and 10x sequencing data will be processed using the standard pipeline (Drop-seq core computational protocol V1.2, <http://mccarrolllab.com/dropseq/>) with minor modifications. For Drop-seq Read1, bases 1 to 12 will be tagged with cell-barcode "XC," and bases 13 to 20 will be tagged with UMI "XM." For 10x Read1, bases

1 to 16 will be tagged with cell barcode XC, and bases 17 to 26 will be tagged with UMI XM. Read2 will be trimmed at the 5' end to remove any adaptor sequence, and the 3' end will be trimmed to remove poly(A) sequences of length six or more and then aligned to human (hg38) genome reference using STAR aligner (STAR_2.5.1a), allowing no more than three mismatches. Gene expression matrix will be then generated using the "MIN_BC_READ_THRESHOLD=2" option to retain UMIs with two or more reads.

J. Statistical Analysis

Quantitative data will be expressed as mean \pm standard deviation (SD)/95% confidence interval (CI) if they follow a normal distribution, median \pm inter-quartile range for skewed distribution. The baseline characteristics of the three groups of patients will be compared using the Mann-Whitney test. Differences between groups will be assessed by Student's t-test, ANOVA and non-parametric test where appropriate. P value of <0.05 will be considered statistically significant. Statistical analysis will be performed using SPSS version 26.0.

K. Consents

All subjects will be given a detailed explanation and their permission will be obtained before they are recruited into the study. A written consent form will be signed by the participants. The participants can withdraw from the research without any repercussions.

L. Ethical considerations

(1) Ethical conduct of the study

Risks of blood sample collection will be minimized. Minor discomfort or worrisome may be implied to the patients if blood sample collection is needed. Supports will be given by research team.

The study will be conducted according to the principles of the Declaration of Helsinki and its most recent updates (7th revision, 2013). Investigator(s) will ensure that the study complies with all local, federal, or country regulatory requirements as applicable.

(2) Confidentiality

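### Both karyotype groups mix miscarriage with termination and the named tests do not adjust for type of loss; sections D and J also disagree on the number of groups

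*Protocol*

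**What the plan says.** Section C admits both types of loss: "Women with miscarriage or TOP who are suitable candidates for MVA". It sets no quota, no matching and no restriction on the reason for TOP.

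Section D defines two groups by karyotype only. The first is "women who miscarry or TOP with chromosomally normal fetus"; the second has the same wording for an abnormal fetus. Hypothesis 1 in section B fits this ("Decidua tissue is different between euploidy pregnancy and aneuploidy pregnancy"), and section E also speaks of two groups.

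The sizing in section D uses pilot CD45+ counts of "89.7 ± 18.3 in decidual samples from miscarried women with abnormal karyotyping" and "102.3 ± 20.2 in miscarriage women with normal fetal karyotyping". Both describe miscarriages. From these, with alpha 0.05 and 80% power, the protocol takes 50 per arm and 100 in total.

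Section J says: "The baseline characteristics of the three groups of patients will be compared using the Mann-Whitney test". For differences between groups it names "t-test, ANOVA and non-parametric test where appropriate". It mentions no covariate or stratum.

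The background states: "Approximately 60% of spontaneous abortions are attributable to numerically abnormal chromosomes". It gives no corresponding rate for TOP. Its purpose statement also mentions gestational-age-matched decidua as a further comparator.

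**The concern.** Karyotype is observed, not randomised. If TOPs make up a different share of the normal and abnormal groups, and leucocyte counts differ between TOP and miscarriage, an unadjusted comparison mixes the two effects. A karyotype difference could then partly reflect type of loss, or a real one could be hidden. Nothing in the protocol makes the abnormality rates equal in the two types of loss, or the decidua alike.

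Two further points do not fit together. The 50 per arm describes a miscarriage-only contrast, whereas the enrolled groups are mixed. And a reader cannot tell whether a third group is intended; if it is, Mann-Whitney cannot compare three groups in one test.

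**Working it through.** **The plan's own figure.** The planned difference is 102.3 − 89.7 = 12.6. The pooled SD is √((18.3² + 20.2²)/2) = 19.27. For a two-sided 5% t-test (the protocol does not state sidedness), 80% power needs 37.7, so 38 per arm. Fifty per arm gives about 90% power. The stated 50 is therefore not reproduced at 80% and leaves slack. A 60/40 karyotype split of 100 women gives 88–89%.

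**Form of the bias.** Let q be the abnormality rate among TOPs and let shift be the TOP mean minus the miscarriage mean. Then

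bias = shift × (TOP share in normal group − TOP share in abnormal group).

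This is zero when q = 60%, the rate taken for miscarriages, or when the shift is zero.

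**Assumed inputs.** The protocol gives no TOP share, no q and no shift, so these are varied. Fixed inputs are N = 100, SD 19.27 and 60% of miscarriages abnormal.

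**Worked cell: 20% TOPs, q = 10%, shift 12.6.**
- Normal group: 80 × 0.4 = 32 miscarriages and 20 × 0.9 = 18 TOPs, so TOP share 18/50 = 36%.
- Abnormal group: 48 miscarriages and 2 TOPs, so 2/50 = 4%.
- Bias = 12.6 × 0.32 = 4.03.
- Variances including the mixture: 371.5 + 0.36 × 0.64 × 158.8 = 408.0 and 371.5 + 0.04 × 0.96 × 158.8 = 377.6.
- SE = √((408.0 + 377.6)/50) = 3.96, so bias/SE = 1.02.
- Rejection with no karyotype effect ≈ 1 − Φ(1.96 − 1.02) + Φ(−1.96 − 1.02) ≈ 17%.

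Simulation of the pooled t-test gives the same figure.

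**All cells at 20% TOPs (simulated).** Null rejection means no karyotype effect. Power means a true effect of 12.6 with the shift always signed to oppose it.

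| q | TOP share, normal vs abnormal | Bias, shift 12.6 | Null rejection, shift 12.6 | Null rejection, shift 6.3 | Power, shift 12.6 | Power, shift 6.3 |
|---|---|---|---|---|---|---|
| 0% | 38.5% vs 0% | +4.9 | 22% | 9% | 49% | 74% |
| 10% | 36.0% vs 4.0% | +4.0 | 17% | 8% | 56% | 77% |
| 30% | 30.4% vs 11.1% | +2.4 | 9% | 6% | 70% | 82% |
| 60% | 20% vs 20% | 0 | 5% | 5% | 86% | 88% |
| 80% | 11.1% vs 25.0% | −1.8 | 7% | 5–6% | 73% | 81% |
| 100% | 0% vs 29.4% | −3.7 | 13% | 7% | 54% | 72% |

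Without TOPs, power is about 88%.

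**Other TOP shares, over all q.** With the full shift, null rejection runs 5–11% at 10% TOPs and 5–35% at 30% TOPs. With half the shift it runs 5–6% and 5–13%.

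**With a type-of-loss term.** Linear regression on karyotype and TOP keeps the error rate at 4.6–5.2% in every cell.

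**Group count.** Section D defines two groups and section E refers to both; section J refers to three and applies a two-sample test. These cannot all stand.

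**The case against.** - **Adjustment belongs in an analysis plan.** Covariates and sensitivity analyses are often left there, that plan is not at hand, and section J does not rule out adjustment. This carries some weight. But the pooled group definition, the named tests, the miscarriage-only sizing and the conflicting group count are all fixed in the protocol, and the tests it names are unadjusted.
- **The bias is conditional.** It needs both an unequal abnormality rate and a decidual difference by type of loss, and the protocol quantifies neither. This stands, and it is why no direction or size is claimed.
- **The figures are illustrative.** They run from no inflation to about 35%, and at 10% TOPs with half the shift the effect is negligible. The power columns show the unfavourable sign at every q. If the sign that opposes the effect below q = 60% is kept, power under the full shift is about 92% and 97% at q = 80% and 100%. The runs also let karyotype split near 60/40, not the planned 50/50. These limits hold.
- **The remedy was tested only against its own target.** Type of loss was the sole simulated confounder, so the restored error rate follows by construction. True; the runs show nothing about other confounders.
- **Miscarriage-only pilot data are a disclosed limitation.** Agreed. With 38 per arm enough for 80% power, no sizing failure is shown.
- **The third group may be leftover wording.** That is plausible. The background's purpose statement describes a trisomy 16 versus 46XY comparison and is weak support for a third group here. The text still needs reconciling.

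**Conclusion.** The concern holds as a point the sponsor should consider, with medium confidence. As written, the karyotype comparison is open to confounding by type of loss, in a direction the protocol does not determine. There is no bias if TOPs and miscarriages have similar abnormality rates, or if decidua does not differ between them. If both differ, the consequence ranges from negligible to a several-fold inflation of the 5% error rate or a substantial loss of power, depending on the assumed TOP share, q and shift. The slack in 50 per arm keeps several cells above 80% power, but a larger sample does not remove confounding.

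The conflict over the number of groups, and the use of Mann-Whitney for three, are wrong as written whatever those assumptions are.

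**What to change.** Keep the pooled karyotype comparison of section D, and:

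1. Record type of loss as a variable. It is known at enrolment because it is part of the inclusion criteria.
2. State in section J that it enters the comparison as a term or stratum.
3. Add the miscarriage-only comparison, which matches the pilot population, as a sensitivity analysis.
4. State in section D that the sizing describes a miscarriage-only contrast.
5. Reconcile two versus three groups across the background and sections D, E and J. If a third group is intended, define it and replace Mann-Whitney with a test for three groups.

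The cost is protocol wording, one recorded variable and some power:

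| TOP share | Adjusted power, same karyotype effect in both types (q = 0–100%) | Adjusted power, effect only in miscarriages (q = 10–80%) | Miscarriage-only analysis |
|---|---|---|---|
| 10% | 85–88% | 81–84% | 84–85% (54 vs 36 women) |
| 20% | 80–88% | 71–77% | 80–81% (48 vs 32) |
| 30% | 74–88% | 59–69% | 74–75% (42 vs 28) |

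The comparison value is about 88% with no TOPs at a 60/40 karyotype split. If the effect exists only in miscarriages, the sensitivity analysis helps to show it.

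### Section D's own pilot figures need 37–38 women per arm for 80% power, not 50; 50 per arm gives about 90%, and a total of 100 does not assure 50 per arm

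*Protocol*

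**What the plan says.** Section D (Sample Size) compares women whose fetus is chromosomally normal with "women who miscarry or TOP with chromosomally abnormal fetus". It sizes the comparison on CD45+ cells: in the pilot, "the CD45+ cell count was 89.7 ± 18.3 in decidual samples from miscarried women with abnormal karyotyping", against 102.3 ± 20.2 where the karyotype was normal. It concludes that "The sample size required for an alpha value of 0.05 and 80% power would be 50 in each arm", and then: "Therefore, a total of 100 subjects will be recruited".

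The section mentions no allowance for lost or unusable samples, no adjustment of alpha, no allowance for a non-parametric test, and no rule for filling each group. Section J lists the tests as Student's "t-test, ANOVA and non-parametric test where appropriate".

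The background section notes that "product of conception derived from USG-MVA can be sent for karyotyping analysis", and Sections G and H describe genetic testing of chorionic villi separated from that tissue. The background also states: "Approximately 60% of spontaneous abortions are attributable to numerically abnormal chromosomes in the developing conceptus".

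**The concern.** This is the protocol's only sample-size justification. It gives means, SDs, alpha, power and a result, so it can be checked completely, and the result does not follow from the rest. A reader cannot tell whether the gap between 38 and 50 is a higher power target, a reserve for unusable samples or a slip. This matters in use: anyone who takes 50 per arm as the minimum for 80% power will misjudge what a shortfall costs.

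The step from 50 per arm to 100 in total also treats the groups as if they were assigned. Fetal chromosomal status is not an eligibility criterion and is learned only after the procedure, so the split is whatever the recruited women produce.

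**Working it through.** **Inputs (Section D).** Means 89.7 and 102.3; SDs 18.3 and 20.2 (± read as SD); alpha 0.05, taken as two-sided because sidedness is not stated; equal groups.

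- Difference: 102.3 − 89.7 = 12.6
- Pooled SD: √[(18.3² + 20.2²)/2] = √(742.93/2) = 19.27
- Standardised difference: 12.6/19.27 = 0.654

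**Attempt to reproduce 50 at 80% power.** Normal approximation, n per arm = (z₁₋α/₂ + z_power)² × (SD₁² + SD₂²)/difference²:

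- 80%: (1.960 + 0.8416)² × 742.93/158.76 = 36.7, so **37**
- 90%: (1.960 + 1.2816)² × 742.93/158.76 = 49.2, so **50**

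Two-sample t-test (noncentral t):

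| n per arm | Power |
|---|---|
| 37 | 79.2% |
| 38 | 80.3% |
| 50 | 89.9% |
| 51 | 90.5% |

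The stated 50 is not reproduced at 80%. It is what the normal approximation returns for 90%.

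**Other readings of the stated inputs, 80% power.**

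- Larger pilot SD (20.2) in both arms: 41 (normal) or 42 (t-test)
- One-sided alpha 0.05: 29 (normal) or 30 (t-test), which widens the gap
- Mann-Whitney test, t-test size divided by relative efficiency: 40 (efficiency 0.955) or 44 (worst case 0.864)

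**What 50 at 80% would need (t-test).** Any one of: an SD of about 22.3, above both pilot SDs; a difference of 10.9 instead of 12.6; alpha of about 0.017; or a loss of 1 − 38/50 = 24%. Section D states none of these.

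**The split of 100.** If each woman independently had a 60% chance of an abnormal result, an exact 50/50 split would have probability of about 1%; at 50% it would be about 8%. The background's 60% covers spontaneous abortions only, and no rate is given for terminations, so the splits below are assumptions. Power with all 100 women evaluable (Student column uses SD 19.27):

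| Abnormal/normal | Student | Welch |
|---|---|---|
| 50/50 | 89.9% | 89.9% |
| 60/40 | 88.7% | 87.9% |
| 70/30 | 84.3% | 82.2% |
| 30/70 | 84.3% | 85.3% |

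Smallest evaluable total for 80% power (Student to Welch): 76 at 50/50, 79–81 at 60/40, 89–95 at 70/30.

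**The case against.** The strongest reply is that the error is on the safe side. Fifty per arm delivers at least the 80% claimed, so no conclusion of the study is endangered by it. That stands, and it limits the point to a correction of the statement.

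A second reply is that 50 may have a legitimate origin. Section J refers to three groups of patients and the background describes a three-way comparison; 0.05/3 = 0.0167 would give 49 (normal) or 51 (t-test) per arm at 80%. The larger SD combined with worst-case Mann-Whitney efficiency would give 48. These are possible origins, and they are a reason not to assume that 90% was the intended power. They do not rescue the sentence, because Section D states alpha 0.05, two groups and no such adjustment.

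A third reply is that unequal groups are normal in an observational comparison and cost little power here. That is true for 100 evaluable women. It is not assured if fewer are evaluable: villi are screened for maternal cell contamination (Section H), and the background says normal female conceptuses were not chosen for study. As illustrations only, with the Welch test, 63/27 gives 77.9%, 48/32 gives 79.7% and 60/20 gives 66.7%. No loss rate is given, so reassurance about power has to be conditional on the number evaluable.

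**Conclusion.** The concern holds. With ± read as SD and a two-sided test, the stated inputs require 37 (normal) or 38 (t-test) per arm for 80% power. The stated 50 is 32% above 38 (50/38 = 1.32) and corresponds to 89.9% power. None of the readings tried above gives 50 at 80%. Whether a 90% target, an undeclared allowance or a slip lies behind it cannot be settled from the protocol.

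It also holds that recruiting 100 women does not assure 50 per group. The consequence is small if all 100 are evaluable and the imbalance is moderate; beyond that, it depends on figures the protocol does not give. The study is not shown to be underpowered. The sample-size statement should be corrected.

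**What to change.** Rewrite the sample-size paragraph in Section D:

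1. Make the numbers agree. Either state that, at two-sided alpha 0.05 with a t-test, 38 evaluable women per arm give 80% power and 50 give about 90%, or keep 50 and name the power target or allowance that takes 38 to 50. Correcting the statement is not in itself a reason to recruit fewer women.
2. Replace the reference to a fixed number in each arm with a statement that group sizes follow from the genetic result and are not controlled.
3. Give power over a range of evaluable splits, labelled as assumptions. For 100 evaluable: about 90% at 50/50, 88–89% at 60/40, 82–84% at 70/30. Add the expected share of unusable samples if one is known.

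The cost is the rewording of one paragraph. The correction itself requires no additional patients.

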All women in both groups will receive identical standard routine care. They will fast after breakfast and be admitted to a day ward for the MVA procedure. USG-MVA will be carried out as a day procedure in an out-patient setting according to a pre-defined protocol. The patient will be given misoprostol 400µg orally for cervical priming 2-3 hours before the procedure. In case of heavy bleeding or passage of products of conception, pelvic examination and/or USG will be performed to ensure that USG-MVA is still indicated. Routine observations, including blood pressure, pulse and temperature are measured. An intravenous catheter (14G) will be inserted. All patients will be given 500mg naproxen orally 1 hour before the procedure. If the woman was allergic to non-steroidal anti-inflammatory drug, paracetamol or codeine will be used instead. The procedure will be carried out with a full bladder.

USG-MVA will be performed using a 60ml charged syringe (MedGyn Aspiration Kit IV, 02511, [name]) with a flexible curette (size 4 to 7 mm, subject to doctor's discretion) attached to it. An experienced doctor and a nurse will perform the procedure together. Transabdominal USG during MVA will be performed using Voluson E730 Expert US system. Before the procedure, paracervical block will be performed using a 23-gauge dental needle syringe to inject 5ml of 2% xylocaine into a depth of 0.5cm at the cervical-vaginal juncture at 4, 5,7, 8-o'clock position to reach the uterosacral ligaments and 5ml of local lidocaine gel (Xylocaine 2%) will be applied to the cervix a few minutes before the insertion of the MVA catheter. The MVA procedure will stop as soon as USG guidance confirmed that the uterine cavity is empty.

F. Blood collection

Patient's extra blood sample will be donated with consent if blood investigation is indicated by doctors. The amount of blood volume is approximately 5-10ml blood samples via the method of venipuncture by trained health workers. Identification of blood sample will be counter-checked with patient and sent to laboratory for immunity check.

G. Sample collection, separation, and preparation

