POCs obtained from MVA procedure were rinsed in normal saline thoroughly in the kidney basin to minimize maternal blood. Chorionic villi were considered as a proxy of fetal genetics, appeared to be yellowish in color and tree-projection-like in appearance, floating on the surface of the waterline. Decidua are originated from the mother, appeared substantive in structure and sank in the basin. The two different types of tissues are separated from each other for different testing.

- (1) Chorionic villi will be divided into two parts: one sent for histopathologic diagnosis as a standard clinical practice, while another aliquot for molecular analysis for a comprehensive genetic etiology investigation. Multiple-site chorionic villi sampling combined with low-pass genome sequencing (FetalSeq) will be performed for detecting site-to-site heterogeneity (the mosaicism phenomenon). For cases that remain genetically idiopathic, mate-pair sequencing (ChromoSeq) and 30x whole genome sequencing (WGS), more superior and high-resolution sequencing platforms will be performed for detecting cryptic structural rearrangements, absence of heterozygosity (AOH), and single-nucleotide variant (SNV).
- (2) The maternal decidua will be divided into two proportions: i) one proportion will be fixed in 4% formalin for 24 hours, routinely processed and embedded in paraffin wax; ii) another proportion will be rinsed immediately and then snap frozen-stored for further analysis if needed. 5 – 10 ml of blood will be taken for immunoassay.

H. Genetic studies on chorionic villi

For each POC sample, chorionic villi with good morphology were randomly biopsied with ophthalmic forceps under the microscope (Leica S6E stereomicroscope, Wetzlar, Germany), avoiding areas of severe blood contamination. All selected chorionic villi will be purified carefully in PBS. They will be finally collected in a 1.5 ml tube for DNA extraction. Genomic DNA (gDNA) will be extracted using a commercial kit DNeasy Blood & Tissue Kit (Qiagen, Hilden, Germany). Multiplex quantitative fluorescence polymerase chain reaction (QF-PCR) was performed on DNA for excluding maternal cell contamination (MCC) and polyploidy.

I. FetalSeq

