(1) SNVs calling is carried out by HaplotypeCaller (GATK) and annotated by ANNOVAR (PMID: 20601685) with different public referenced databases. SNV interpretation is performed by referencing the medical literature and online databases according to the guidelines of the ACMG.

(2) For CNV, SV, and AOH analysis, the same pipeline used in ChromoSeq method is applied.

I. Immunological studies on maternal decidua

I. Immunohistochemistry staining

Serial sections will be stained with anti-CD56 antibodies for uNK cells or anti-CD163 antibodies for macrophages. Also, other leucocytes will be determined by immunohistochemistry as well. All primary antibodies will be incubated overnight at 4 °C. The reaction will be developed with 3,3-diaminobenzidine (DAB) containing 0.01% H₂O₂ to give a brown reaction product. Sections will be lightly counterstained with haematoxylin, dehydrated, cleared and mounted with DPX synthetic resin.

II. Multiplex immunofluorescence panel of different immune cell markers

After immunohistochemistry analysis was used for all of the target decidua markers (including different leucocytes), each target was assessed by a uniplex immunofluorescence assay by the Opal 7-color kit to optimize the antibodies and to build up spectral libraries for multiplex immunofluorescence. Slides will be scanned and images will be acquired using the Vectra 3.0 spectral imaging system. The data from the multispectral camera will be accessed and all the leucocytes population from each panel will be characterized and quantified by the imaging InForm software.

III. Serum cytokine measurements

Serum will be separated by centrifugation at 3000 rpm at 4 °C for 10 min and stored at – 80 °C freezers for later measurements. Later, the maternal serum samples will be thawed and centrifuged for measurements of all cytokines and chemokines at the

same time. The Luminex's xMAP® technology, a multiplexed microsphere-based cytometric assay, will be used to examine.

IV. Multicolor flow cytometry

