The decidual sample will be transferred into 10 ml RPMI 1640 (Sigma Aldrich UK) and transported to a single laboratory facility, without delay. The decidual sample will be passed through a 70-µm nylon filter (BD Falcon™, BD Biosciences, UK) to remove it from RPMI and associated blood, blotted and accurately weighed. Samples will be standardised to approximately 300 mg of tissue whenever possible. Mechanical dissociation will be applied, using Gentle MACs™ C tubes (Milteny Biotech) and 10 ml fresh RPMI to efficiently release all cells, using a preset function (Program C for 30 s, Program B for 30 s) designed as suitable for decidual tissue. The free cell lysate will be then passed through a 40-µm nylon filter to isolate connective tissue elements above this size, pelleted at ×500 g, and re-suspended to a final volume of 1.5 ml in BD staining buffer (BD Biosciences, UK). Two-hundred microliters of resuspended cells will be then incubated with the antibody cocktails (CD56, CD16, CD57, CD14, CD38, CD3, CD4, CD8, CD69, HLA-DR, CD28, CD15, CD33, CD66b Fox-3, PD-1, Tim-3, CTAL-4, IL-10, IL17, TGF-β, etc.). In parallel, the red blood cells of peripheral blood will be lysed by RBC lysis buffer and stained with the antibody cocktails. The antibody cocktails will be standardised to a final volume of 100 µl with BD staining buffer. Flow cytometric evaluation will be followed using co-localisation of these specific antibodies by multicolour/multitube flow cytometry.

V. Single-cell capture, library preparation, and sequencing

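### Do Sections F and G conflict on who gives the research blood sample, so that the serum and blood analyses need a new rule?

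*Protocol*

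**What the plan says.** Section F (Blood collection) sets two conditions for the research sample, consent and a clinical reason: "Patient's extra blood sample will be donated with consent if blood investigation is indicated by doctors". It gives a volume of 5-10 ml, taken "via the method of venipuncture by trained health workers".

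Section G (Sample collection, separation, and preparation), at the end of the item on handling decidua, repeats the volume without either condition: "5 – 10 ml of blood will be taken for immunoassay".

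Two items of the section on immunological studies of maternal decidua use blood. Item III (Serum cytokine measurements) says "the maternal serum samples will be thawed and centrifuged for measurements of all cytokines and chemokines". Item IV (Multicolor flow cytometry) says "In parallel, the red blood cells of peripheral blood will be lysed by RBC lysis buffer and stained with the antibody cocktails". Neither says which women contribute.

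Section L (Ethical considerations) is again conditional, in a statement about risk: "Minor discomfort or worrisome may be implied to the patients if blood sample collection is needed".

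Section B frames the immune objective in terms of decidua, and Section D sizes the study on decidual CD45+ counts, with 50 women per arm and 100 in total. Neither gives a number for blood.

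**The concern.** Sections F and G can be read as two different collection rules. Under the first, blood comes only from women for whom a doctor ordered a test; under the second, it comes from everyone. The protocol does not define an indication, say how often one arises, or give a draw time relative to the misoprostol and naproxen in Section E.

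If Section F applies, any comparison of serum or peripheral-blood markers by karyotype group rests on a clinically chosen subset of unknown size. Two things would be at stake. One is precision, because fewer than 50 per arm would be available. The other is bias, if the reason for ordering a test were related both to immune markers and to karyotype. The mix of miscarriage and termination of pregnancy is a conceivable route, since both are eligible and the reasons for blood tests may differ between them. An analysis plan written later could not recover samples that were never drawn.

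**Working it through.** **1. Is there a contradiction?**

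| Place | Role of the text | Condition on blood |
|---|---|---|
| Section F | Dedicated blood-collection section | Consent and a doctor's indication |
| Section G | Tissue handling; closing line on blood | None stated |
| Immunological studies, III and IV | Laboratory methods | None stated |
| Section L | Statement of discomfort risk | Blood mentioned as contingent |

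Section F is the only place that sets out to say from whom blood is taken. Section G repeats its volume and adds the use. Reading Section G as subject to Section F makes all the texts compatible. Item III refers to whatever maternal serum samples exist, and the parallel processing in item IV describes laboratory workflow. Section L fits Section F but is weak evidence, because a risk statement does not define a sample. What remains is a condition left unrepeated in Section G and the word for a clinical indication left undefined.

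**2. What depends on blood?** Both objectives, both hypotheses and the sample size concern decidua or conceptus genetics. Section J speaks only of differences between groups in general. A karyotype comparison of blood markers is a reasonable inference, but no blood endpoint is specified.

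**3. Does the text point to bias?** Karyotype is determined from villi obtained at the procedure, so in general it is not known when blood is ordered. Section C excludes clinical sepsis and bleeding disorder and requires haemodynamic stability, which removes several obvious reasons for a test that bear on immune state. Section E gives all women in both groups identical routine care. A link through miscarriage versus termination remains possible but is not shown.

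**4. How large could the loss of precision be?** Inputs from Section D: means 102.3 and 89.7, SDs 20.2 and 18.3, 50 per arm, alpha 0.05 (taken as two-sided). Assumptions of this check: an even split, the same share sampled in both groups, and shares of 100%, 70%, 50% and 30%.

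- Pooled SD = √((18.3² + 20.2²)/2) = 19.27
- Standardised difference d = (102.3 − 89.7)/19.27 = 12.6/19.27 = 0.654

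The plan's own figure first: at 80% power the normal approximation, n = 2(1.960 + 0.842)²/0.654², gives 37 per arm. The stated 50 corresponds to 90% power. That is a separate matter and has no bearing on who gives blood.

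Smallest detectable difference at 80% power: approximately d = (1.960 + 0.842)·√(2/n). Values from the noncentral t distribution are slightly larger. The last column is the noncentral t power at d = 0.654, which borrows the decidual effect purely for illustration.

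| Share sampled | n per arm | Detectable d, approximate | Detectable d, noncentral t | Power at d = 0.654 |
|---|---|---|---|---|
| 100% | 50 | 0.56 | 0.566 | 0.899 |
| 70% | 35 | 0.67 | 0.679 | 0.769 |
| 50% | 25 | 0.79 | 0.809 | 0.620 |
| 30% | 15 | 1.02 | 1.060 | 0.409 |

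The arithmetic is sound, but its key inputs are assumed. The protocol gives neither a sampled share nor an effect size for any blood marker, so the table bounds what might happen and does not show a loss in this study.

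**The case for a change.** The best argument for a change is that who is bled is a collection rule, not an analysis detail. The protocol expresses it in two ways, and no later document can restore samples that were not taken. Consent does not explain the gap, because Section F adds a clinical indication on top of it. If Section F governs, the laboratory items do not disclose that their results come from a selected group. Draw time is also open in a study that gives an anti-inflammatory drug before the procedure and measures immune markers.

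Part of this stands. The wording differs between Sections F and G, and the indication is undefined. The rest carries less weight. Draw time is an omission, since no text conflicts with another on it; it can sit in a laboratory manual, and nothing suggests that it would differ by karyotype group.

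The remedies also gain little. Taking blood from every consenting woman would mean draws where no test is indicated, together with revised consent and ethics wording. That would be a trade-off against Section L's aim of keeping the risks of blood sampling low. Tying the draw to the catheter in Section E ("An intravenous catheter (14G) will be inserted") would not by itself fix the time, because no clock time is given for its insertion. The lighter remedy, stating how many women gave blood in each group and treating those results as exploratory, is ordinary reporting for a measurement outside the objectives.

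**Conclusion.** No change to the plan is needed. The difference between Sections F and G is real but clerical in weight: the dedicated section states the condition and a later line does not repeat it. The decidual comparison, the genetic objective and the sample size are unaffected. Following the protocol as written gives no demonstrably wrong result.

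The blood results may rest on fewer than 50 women per arm, with a detectable standardised difference between 0.57 (all sampled) and 1.06 (30% sampled), under equal sampling in two arms of 50. Bias would need an indication related to both karyotype and immune markers, which the protocol does not show.

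This conclusion rests on reading Section G as subject to Section F, and on the blood measurements being supplementary, as Sections B and D imply. It would need another look if a serum or peripheral-blood marker were made a formal endpoint.
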